[name], [name], and [name] will speak to the medical geneticists identified at genetics conferences and those identified using direct outreach by phone or in person. Geneticists who are interested in participating will be e-mailed a secure link to the REDCap-hosted survey. The first page of the survey will contain the informed consent form for potential participants to review. They will also have the opportunity to contact [name], [name], [name], and other project leaders about participation in this study. After reviewing the informed consent language on the survey, the geneticists will electronically provide consent for participation via the REDCap-hosted web survey. Consent records will be stored securely on the REDCap server.

Patients

Both Primary Care and Cardiology

Prospective patient participants will meet with a member of the study staff in the BWH Center for Clinical Investigation to discuss the study and review the consent form [**see attached patient consent form—primary care and –cardiology**]. The informed consent meeting will last approximately 30 minutes. Prospective participants who wish to participate will sign the consent form. Should prospective participants need additional time to decide whether or not to participate in the

study, the study staff will provide the consent form for the participant to take home and will follow-up one week later with the prospective participant to schedule a second appointment to review and sign the consent form in person. Patients who decide not to participate will not be contacted again, but reasons for decline will be documented **[see attached study decline log – patients]**. The MedSeq Project Manager will store the signed consent forms in a locked file cabinet in her office.

The study staff will randomize the patient to either receive WGS or not (Standard of Care) **[see attached randomization schema]** after the first in-person visit. All patients will be blinded to randomization status until the results disclosure session.

Recruitment in Primary Care and Cardiology will cease once each physician enrolls approximately 10 patients.

In the event of loss to follow-up or patient withdrawal, we will reinstitute recruitment procedures to meet our goals of having 100 patients randomized to receive WGS and 100 patients randomized to not receive WGS who all complete the 6-month follow-up. We plan to recruit and enroll 300 patients in order to ensure that 200 complete the full follow-up.

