After the patient leaves the BWH CCI, the study staff will randomize the patient to either the intervention (WGS+) or the comparison (WGS-) arm **[see attached randomization schema]**. The patient will remain blinded to the randomization until the results disclosure session. All blood samples will initially be sent to the Partners Laboratory for Molecular Medicine (LMM). Then, one tube of blood will be shipped to Illumina, Inc. for WGS and one tube of blood will be sent to the BWH Blood Bank for red blood cell antigen phenotyping. The LMM will retain one tube of blood for any necessary Sanger sequencing confirmation prior to reporting the results. If the patient is randomized to the comparison arm, both tubes of blood will be safely discarded.

Next the study staff will contact the participants to set up a time to complete the baseline qualitative interview **[see attached baseline qualitative interview guide – patients]**. All interviews will be conducted at the BWH CCI, be audio-recorded and will last approximately one hour. The audio-recordings will be de-identified, electronically stored on the MedSeq Project Manager computer and shared with the study investigators at Baylor College of Medicine and Duke University. Upon completion of the qualitative interview, the participant will receive \$40.

Once the physician has received the Genome Report and/or Family History Output, he or she will schedule the results disclosure session with the patient directly. The physician will alert the study staff of the appointment date and time. The physician will disclose the results to the patient. Patients in the Primary Care will either receive a Family History Output alone (comparison arm/WGS-) or a Family History Output and a Genome Report (intervention arm/WGS+) **[see attached randomization schema]**. The results disclosure session will take place in either the physician's clinic, office or the BWH

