CCI. The results disclosure session will be audio-recorded. The audio-recordings will be de-identified, electronically stored on the MedSeq Project Manager computer and shared with the study investigators at Baylor College of Medicine and Duke University, which are both funded research subcontracts of this grant to analyze the audio-recordings generated from this project. During the results disclosure session, the physician will review the patient's family history with the patient for accuracies, gather additional information that the patient did not enter previously, and analyze, interpret and discuss the family history with the patient. The physician will make notes about the patient's family history and place the Output and their notes in the medical record. After the results disclosure visit, the physician will place the Genome Report and/or the Family History Report in the patient's medical record.

After the results disclosure session, the study staff will meet with the patient either at the BWH CCI or in the physician's clinic or office (space permitting) and administer the results disclosure survey **[see attached results disclosure survey]**. This survey will take approximately 30 minutes to complete. The study staff will immediately review the scales assessing depression and anxiety (The Hospital Anxiety and Depression Scale (HADS)). Should a patient score above our pre-specified cut-off scores for this scale, the study staff will alert the PI and the genetic counselor. The genetic counselor will call the patient after the visit, review the elevated score with the patient and ask questions to monitor the safety and well-being of the patient. The genetic counselor will document this conversation **[see attached Safety Monitoring Chart Note]**, and review the case with the PI. The PI and the genetic counselor will make appropriate referrals to the patient's primary care physician and/or a mental health professional as needed. All cases of safety monitoring will be reviewed by the IRB and the MedSeq Project Monitoring Committee according to our AE reporting protocol **[see attached AE reporting/MPMC schema]**.

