After all 6-month follow-up visits are complete, the study staff will review each patient's medical record to collect data regarding tests, procedures, referrals, etc. that have been initiated post-results disclosure. To conduct this medical record review, we will utilize the Partners Research Patient Data Registry (RPDR) as well as manual chart reviews.

Additional African American/African participants recruited in the extension phase of the study will all be placed in the whole genome sequencing arm of the study. They will undergo the same activities as the traditional MedSeq participants.

For Patients who we have identified to have a monogenic finding, that is a finding that could potentially impact their health risk, we plan to perform additional analysis. We will review their medical records looking, specifically with their variant in mind, to see if features associated with the variant were known prior to the study or were identified by further testing or by their physician during the course of the study. For individuals we feel may need further work-up we will contact them to offer them the option of coming in for additional phenotyping. If interested participants will sign the updated consent, which includes information about this visit and what will be included, **[see attached Physician Consent Form_Primary**

Care_extension 12.14.15]. If participants consent to participate, they will come in for a physical exam conducted by a clinical geneticist, [name] or [name] in the BWH CCI. They will have a more extensive family history collected by a certified genetic counselor and/or web-based program. We may also ask them to sign a release of medical records so that study staff can review medical records both within and outside the Partners Health Care System to determine if they have any known features associated with their genetic variant. The goal of this visit will be to determine if they have any previously undetected signs and symptoms of their genetic variant. We may also refer these participants for additional tests or imaging procedures relevant to their genetic variant. If associated features are identified follow-up recommendations will be made to the participant and their MedSeq provider in the form of a clinic note entered into the electronic medical record.

Cardiology

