After the six week- and six-month follow-up surveys are complete, the study staff will immediately review the scales assessing depression and anxiety (The Hospital Anxiety and Depression Scale (HADS)). Should a patient score above our pre-specified cut-off scores for this scale, the study staff will alert the PI and the genetic counselor. The genetic counselor will call the patient after the visit, review the elevated score with the patient and ask questions to monitor the safety and well-being of the patient. The genetic counselor will document this conversation **[see attached Safety Monitoring Chart Note]**, and review the case with the PI. The PI and the genetic counselor will make appropriate referrals to the patient's primary care physician and/or a mental health professional as needed. All cases of safety monitoring will be reviewed by the IRB and the MedSeq Project Monitoring Committee according to our AE reporting protocol **[see attached AE reporting/MPMC schema]**.

All subjects will be invited to participate in an additional qualitative survey at the six-month time point **[see attached 6-month qualitative interview guide – patients]**. Study staff will coordinate a time for the in-person qualitative interview. All interviews will be conducted at the BWH CCI, be audio-recorded and will last approximately one hour. Patients who complete the qualitative interview will receive an additional \$40.

For any subject who withdraws from the study at any time, the study staff will complete a form documenting the reason for withdrawing from the study **[see attached withdrawal form]**.

Should a patient withdraw from the study prior to having their results disclosed to them by their physician, we will destroy the Genome Results report.

After all 6-month follow-up visits are complete, the study staff will review each patient's medical record to collect data regarding tests, procedures, referrals, etc. that have been initiated post-results disclosure. To conduct this medical record review, we will utilize the Partners Research Patient Data Registry (RPDR) as well as manual chart reviews. For patients enrolled at BCH, medical records will be reviewed under the direction of [name] (co-PI of the MedSeq project and site-PI of MedSeq at BCH).

We will keep audio and video recordings for 10 years after the completion of the study.

Optional GenomeConnect Validation Study:

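### Services found only by manual chart review may be captured more fully in the WGS+ arm, because abstraction is unmasked and the item list is open; an arm-blind RPDR count should stand beside the combined count

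*Combined protocol and SAP*

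**What the plan says.** **Who collects.** In V. Study Procedures (Patients, Primary Care and Cardiology), "the study staff will randomize the patient to either the intervention (WGS+) or the comparison (WGS-) arm". The record review after the six-month visits is also assigned to study staff, in both patient groups and again under Economic Analysis of Utilization Data in section VI. For Boston Children's Hospital the plan adds: "For patients enrolled at BCH, medical records will be reviewed under the direction of" the site lead.

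**What is collected.** The target is each patient's "medical record to collect data regarding tests, procedures, referrals, etc. that have been initiated post-results disclosure". The list is open at its end. A start point is given (disclosure) but no closing date for the individual patient. Many other instruments in the protocol are cited as attachments; no abstraction form is cited for this review.

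**From which sources.** "we will utilize the Partners Research Patient Data Registry (RPDR) as well as manual chart reviews". Nothing says which source prevails, or whether the two are reported separately.

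**Masking.** IV. Subject Enrollment states: "All patients will be blinded to randomization status until the results disclosure session". No section describes masked or independent abstractors.

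**What the chart shows.** In Primary Care, after disclosure, "the physician will place the Genome Report and/or the Family History Report in the patient's medical record". The Cardiology section likewise has the Genome Report filed, along with the targeted cardiomyopathy report and notes of the family-history review.

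**What the data are for.** Section VI treats the effect of genomic information on health care costs as a critical question and plans a cost-consequences analysis shown as a table.

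**The concern.** Manual abstraction of an open list depends on how hard and where the abstractor looks. A WGS+ chart holds a Genome Report naming disease variants, carrier states, risk alleles and drug-response associations. It tells the reviewer the arm and suggests what follow-up to search for. A comparison chart offers fewer leads. If that leads to more complete capture in WGS+, the table shows extra services that reflect search effort and not extra care.

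The likely direction is toward higher use and cost after sequencing, which is the answer the economic analysis is meant to inform. Enrolling more patients would not reduce such a bias, and a single aggregated table would not reveal it. With no closed list, common form or source rule, a reader could not separate the component open to this problem from the component that is not.

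**Working it through.** The plan gives no power, error rate, mean, standard deviation or capture figure for use or cost, so there is no planned figure to reproduce. The check asks how large an apparent excess could arise when true use is equal in both arms.

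**Inputs**
- m: share of services found only by manual review. Not in the documents; assumed 10% to 50%.
- cW, cC: manual capture rates in WGS+ and WGS-. Not in the documents; assumed 95% v 85%, with 100% v 70% as an extreme.
- Services in RPDR: taken as captured equally in both arms, because a registry query does not depend on the abstractor's knowledge of the arm.

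**Formula**

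Observed ratio WGS+/WGS- = [(1 - m) + m·cW] / [(1 - m) + m·cC]

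**Central cases, 95% v 85%**
- m = 20%: (0.80 + 0.20 × 0.95) / (0.80 + 0.20 × 0.85) = 0.990 / 0.970 = 1.021, a false excess of about 2%.
- m = 50%: (0.50 + 0.50 × 0.95) / (0.50 + 0.50 × 0.85) = 0.975 / 0.925 = 1.054, about 5%.

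**Range**

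| m | 95% v 85% | 100% v 70% |
|---|---|---|
| 10% | 1.010 | 1.031 |
| 20% | 1.021 | 1.064 |
| 30% | 1.031 | 1.099 |
| 50% | 1.054 | 1.176 |

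**Limits of the formula**
- If cW = cC, the ratio is 1.00 for any m.
- If m = 0 (everything comes from RPDR), the ratio is 1.00 whatever the manual capture rates.

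The bias therefore needs both a manual-only share and unequal manual capture. These are ratios of service counts. Reading them as cost ratios also assumes that manual-only services cost, on average, the same as coded ones.

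**The case against.** The strongest reply is that this is an exploratory study. Section VI says the sample is too small for valid cross-group comparisons, and the cost analysis is a descriptive table. That stands: the effect is on how the table is read, not on a test. It does not remove the point, because the same section says differences will still be explored across all study groups, and it gives the cost question prominence.

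Four stronger readings are tempting, and the documents do not support them.

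- **A reader might apply the capture gap to every service.** At 95% v 85% that would give 0.95 / 0.85 = 1.118, about a 12% excess, and invite a claim of an inflated false-positive rate. This would require m = 100%, as if RPDR found nothing. The plan uses RPDR as well as manual review, and no between-arm cost test is specified whose error rate could be inflated.
- **A reader might infer that the same individuals randomise and abstract.** The term used for both tasks is a group label. No separation of roles is stated, but identity is not stated either.
- **A reader might infer that comparison charts contain no prompts.** In primary care both arms have a family-history discussion with the physician's notes filed. Cardiology comparison charts also hold the targeted genetic report. The difference is one of degree.
- **A reader might count the extension's extra record search as part of the problem.** For patients with a monogenic finding the plan says "We will review their medical records looking, specifically with their variant in mind". That review serves a separate phenotyping aim, and nothing says its findings enter the cost table.

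Two further points in the plan's favour stand. Whether a service was initiated after disclosure is a matter of timing against a session that both arms have; it does not ask the abstractor to attribute the service to the genome result. Also, up to three comparison patients who win sequencing in the lottery stay in the record review, which could pull slightly the other way.

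**Conclusion.** The point holds for the part of utilisation that only manual review can find. Abstraction is not stated to be masked, the list is open, the chart shows the arm, and the two sources are combined without a rule. Fuller capture in WGS+ is plausible and would inflate the descriptive comparison of use and cost. The RPDR part is not exposed, provided that the same extraction is run for both arms.

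The size cannot be derived from the documents. Under assumed manual capture of 95% v 85%, the false excess is about 2% at a 20% manual-only share and about 5% at a 50% share. It is zero if capture is equal or if everything comes from RPDR. This is a modest but avoidable weakness in a comparison the plan calls critical. It merits a change because the remedy uses a source already planned.

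**What to change.** In the record-review paragraphs of V. Study Procedures (Primary Care and Cardiology) and in Economic Analysis of Utilization Data:

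1. Run one RPDR extraction for all randomised patients, with one code list and the same post-disclosure window for everyone, without the arm variable. For Boston Children's patients, make an equivalent extract from that site's record with the same codes and window.
2. Restrict manual review to a closed list of items, recorded on one form used alike in both arms.
3. Report the coded-only and the combined (coded plus manual) results side by side, by arm. An arm difference that appears only in the combined result then shows as coming from manual review. It could be real uncoded care or uneven searching, and should be described as such.
4. State that findings made only through the variant-directed extension review do not enter the count.

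Do not rely on giving abstractors an ID list without allocation. Anyone who opens a chart containing the Genome Report sees the arm.

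**Cost.** SAP wording and one extraction from a source already in the plan, plus the parallel Boston Children's extract; no extra staff should be needed. The drawback is that the coded-only count misses some uncoded items, possibly including referrals. The documents do not describe RPDR's contents, so how many is unknown, but the combined result still shows them. The five-year follow-up uses a similar mix of RPDR and manual review, and the same rule could be carried over.

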Illumina's Individual Sequencing Service is a CLIA-certified laboratory test, which includes variant calling and SNP array genotyping for quality control. Once a patient's sequence is complete, Illumina will send the patient's raw genomic data, variant calls and the SNP array data to the CLIA-certified Partners Laboratory for Molecular Medicine (LMM) on an encrypted hard drive. The LMM will store each patient's data on their secure servers currently used to house clinical whole genome/exome sequencing data. The LMM will then share the genomic data set with the MedSeq Project Investigators at the Harvard Medical School Center for Biomedical Information (CBMI) who will evaluate variants in the data set relevant to cardiac disease. The investigators at the CBMI will generate a list of cardiac disease variants and send to the LMM. The LMM will evaluate the genomic dataset sent from Illumina and the list of cardiac disease variants sent from the CBMI. The LMM will then generate the appropriate reports for each patient. There will be two sections of the Genome Report: 1) The General Genome Report, which will include highly penetrant disease mutations, carrier status for recessive disease, disease-associated risk alleles and pharmacogenetic associations and 2) The Cardiac Risk Supplement, which will contain any piece of genetic information found in the genome that is relevant to the care of a patient with cardiac disease or at risk for cardiovascular disease (depending on whether the Genome Report is delivered in Cardiology or Primary Care) [see **attached sample Genome Report**]. Through standard clinical reporting mechanisms currently in place at the LMM, a board-certified geneticist will sign-off on all reports prior to release. The MedSeq Project

study staff will distribute all Genome Reports and Family History Outputs to the physicians via Partners Secure File Transfer. After the disclosure, the LMM will send the Genome Report to the patient's medical record. All results returned to subjects and entered into their medical record will be limited to tests that are CLIA-certified. All reports will be labeled with the patient's name, date of birth and gender per standards analyzing WGS information [**see attached sequencing and reporting schema**].

Procedures in the event of a deceased participant in the Whole Genome Sequencing Arm

In the event that a patient participant has been randomized to the whole-genome sequencing arm, and the patient has passed away prior to results disclosure the study team will consider releasing these results to the participant's family. We believe this is important as genetic results could have implications for other family members.

The research team will speak with the participant's study physician, who can potentially provide background information about the patient participant and their family. Our outcomes team will then review the deceased patient participant's survey and interview data, if applicable, to make sure there isn't anything in our data that would suggest that the patient participant would not have wanted the results to be offered to their family members (e.g. in the baseline survey the patient participant indicates that he or she would not share results with family members). If based on this information the MedSeq Project Executive Committee and Protocol Monitoring Committee and the patient's MedSeq physician sees no indication that the deceased participant would not want their results shared, we will notify the IRB of this information as well as our disclosure plan and seek permission to update the family with these results. If the IRB is in agreement with the individualized plan, we will provide this to the appropriate family member(s) in conjunction with this plan.

Access will be provided to the Genome Resource Center in the event that the physician has any questions prior to communicating with the family.

Additional related research studies

The TradeSeq Study (PI, [name] at University of California, San Francisco) seeks to explore key factors influencing the benefit-risk tradeoffs of whole genome sequencing testing. The TradeSeq Study will interview a subset (n=20) of patients from MedSeq at the baseline visit. The MedSeq Project study staff will ask the participant if he or she is interested in participating in this additional interview. If the participant agrees, the MedSeq Project study staff will conduct the interview [**see attached TradeSeq interview guide**]. This interview will be audio-recorded, and the de-identified audio-recording will be shared with the investigators at UCSF for analysis. The TradeSeq Study investigators at the University of Calgary and a research company called RTI International (who are developing the survey for the UCSF investigators) will listen-in to the interview by phone in order to monitor data collection. These interviews will be used to develop a later survey of all the MedSeq Project participants. The MedSeq Project study staff will coordinate all aspects of the TradeSeq Study in terms of participant contact. Only a de-identified dataset will be shared with investigators at UCSF.

During the post-disclosure follow-up period, the MedSeq Project staff will coordinate a mailing of the TradeSeq Study survey. The survey will be accompanied by a letter from [name] inviting the MedSeq participants to complete the survey [**see attached TradeSeq Invitation Letter**]. The surveys will be mailed to the MedSeq Project study staff at Brigham and Women's Hospital, and de-identified survey data will be shared with the investigators at UCSF.

De-identified data from the MedSeq Project surveys and interviews will be shared with the investigators at UCSF in order to inform the TradeSeq Study analyses.

The CSER ACMG 56 Secondary Findings Project

The CSER ACMG 56 secondary findings project is a consortium wide project being undertaken by the Clinical Sequencing Exploratory Research Consortium (CSER). CSER is the NIH consortium that the MedSeq Project is part of. This ACMG 56 secondary findings project has IRB approval by the NIH. The goal of this project is to: To delineate health care utilization among recipients of secondary variants. To explore communication of variant information to at-risk relatives. To explore perceptions of participants' assessment of the benefits and harms of receiving a secondary variant. A brief overview of this project is attached [**CSER ACMG 56 Interview Project**]. MedSeq Project participants have consented for contact regarding future research studies. The MedSeq Project Manager will call the MedSeq participants who received Whole Genome Sequencing as part of the MedSeq study and who received a variant in one of the genes on the ACMG 56 list, to assess their interest in participating in this CSER interview project using the provided phone script [**CSER ACMG 56 Phone Script**]. For those who express interest in participating, their name and phone number will be provided to the NIH genetic counselor/investigator, [name], and the study will be conducted as approved by the NIH IRB.

Pilot testing of Genome Reports and Study Surveys

Partners Healthcare System genetics clinics offer clinical whole genome and whole exome sequencing to select patients for genetic diagnosis. These clinics have sequenced a number of genomes to date and expect to sequence additional patients in the future. The patients are consented to undergo Whole Genome Sequencing for clinical purposes, but they have not consented to having their genomic data shared with other research investigators. While the process of interpreting a genome is inherently the same as sequencing individual genes and analyzing, interpreting and reporting variants found in these genes, the mere volume of work involved when analyzing, interpreting and reporting variants from a whole genome is much larger than when examining just a single gene. Thus, it would be beneficial for the MedSeq Project investigators at the LMM to pilot test and hone the workflow of this extensive and time-consuming process on several existing genomes.

In order to pilot test the creation of the Genome Report and pilot test the study surveys, Partners physicians will approach their own patients who have already had their whole genome sequenced to utilize their sequencing data to pilot the creation of the MedSeq Project Genome Report. Approximately 25 patients will be approached. The patient will first be approached by their own physician (a physician with genetics expertise in the Partners Healthcare system who cares for the patient whom already had his/her genome sequenced). If the patient is interested in learning more, the physician will ask verbal permission of the patient to forward his/her name and contact information to the MedSeq Project study staff. The MedSeq Project study staff will then review the details of the study with the patient and set up a time to conduct an in-person consent. The patient's physician will be alerted if the patient enrolls in the study. Additionally, through the consent process, the study staff will ask the patients if they would be interested in pilot testing some survey questions that will be featured in the MedSeq surveys, given their experience already having their genome sequenced **[see attached MedSeq Project/Genetics Clinic consent form]**. The MedSeq investigators are interested in piloting the surveys on these patients who have previously underwent whole genome sequencing to see how a representative population answers certain questions. The study staff will inform them that participation is completely voluntary, let them know they can stop at any time, and remind them that this will not be included in the study data or released to any investigators beyond survey development/refinement.

In return, the MedSeq Project would generate a Genome Report to return to patient via their clinician in the clinical setting. The MedSeq Project patient consent form has been modified for this mechanism of returning Genome Reports to patients in genetics clinics **[see attached MedSeq Project/Genetics Clinic consent form]**.

Procedures for individual variant interpretation

Currently, there is no universally implemented systematic method that clinical molecular laboratories use to evaluate variants, and molecular laboratories currently use a combination of the medical literature, existing tools, such as PolyPhen, SIFT and OMIM, and even the laboratory's past experience and judgment when reporting variants to patients. The MedSeq Project investigators and staff at the LMM will utilize similar principles in approaching the interpretation and reporting of variants discovered through whole genome sequencing. Just as the sequencing of one gene or a panel of a number of genes generates a list of variants, falling on a continuum from very well-established to novel, whole genome sequencing will also generate variants on this continuum. Since the MedSeq Project seeks to explore the clinical reporting of large amounts of genomic data with different levels of maturity in terms of evidence and known clinical significance, the Genome Report will contain variants with three levels of evidence for clinical significance: 1) Variants that meet established standards for pathogenicity 2) variants that have been associated with cardiac disease through GWA studies and 3) variants that are predicted to be pathogenic or possibly pathogenic in silico, or are plausibly linked to a clinically relevant molecular cardiac pathway. Through this process, the MedSeq Project will test a new paradigm in genomic medicine where reports include genomic information with differing levels of maturity. The physicians will be educated on the different levels of evidence for variants in the Genome Report, and the Genome Report will include statements regarding levels of evidence for particular variants to guide the physicians. Additionally, the physicians will have the Genetic Resource Center available to answer questions about particular variants listed on the Genome Report. Although some of the information included on the Genome Report will be very new, the MedSeq Project investigators firmly believe that the era of genomic medicine will be a constant cycle of discovery and validation, the clinicians of the near future will constantly be incorporating new genomic information into the care of patients. Thus it is important to begin testing this paradigm in the context of integrating whole genome sequencing information into the current practice of medicine.

Data Sharing

Data Sharing through NCBI dbGaP: Consistent with the NHGRI goals of deriving ongoing value from large scale

sequencing studies, we plan to share both phenotypic and genotypic study data with other investigators, through the NCBI database of Genotypes and Phenotypes (dbGaP). We will use secure file transfer protocol (SFTP) to upload study meta data in the form of a data dictionary, phenotype data, and sequence read archives (SRAs) resulting from this research to dbGaP.

Provision of access: Investigators that wish to use study data on de-identified outcomes will seek access by contacting the MedSeq Project Executive Committee. Once an investigator has submitted a proposal for data access, we will consider the request using successful procedures employed by the PI in prior NHGRI-funded clinical trials. In brief, inquiries related to data sharing will be received and evaluated by the Executive Committee. Investigator proposals will be evaluated and a specific de-identified dataset containing the variables needed for that particular analysis will be shared with the applicant scientist. We will look for guidance from NHGRI, NHLBI the U01 Cooperative Agreement Consortium on whether to provide access to individual-level phenotypic study data or linked phenotype/genome data in the interest of patient privacy. If patients choose to co-enroll in the Partners Biobank, their sequencing data generated through MedSeq will be shared with the Partners Biobank.

VI. Biostatistical analysis

Given the lack of prior research in this area, and the broad number of topics of interest, the aims of the study are predominantly exploratory. This study is designed as a randomized clinical trial of WGS disclosure, but we do not have a large enough sample for statistical power to make valid cross-group comparisons. Nevertheless, we will explore differences in all domains across all study groups.

Qualitative Analyses

[name] at Baylor College of Medicine will lead coding and analysis of qualitative data. Data will be coded and analyzed using both conventional and directed content analysis.²⁷ Directed content analysis will focus on classifying the data according to core ethical principles. Conventional content analysis will allow for identification and classifications of recurring themes in participant responses. All data will be reviewed for competing or alternate meanings or interpretations.²⁸ We will also mark illustrative quotations that convey in illuminating detail how participants think and feel about receiving WGS results and how they have been affected by the information provided.

Analysis of Audio-Recorded Disclosure Conversations

For the analyses of the audio-recorded visits, we will digitally record to audio “.wav” files and they will be coded using the state-of-the art communications analysis system ENCOUNTER program. All coding will be conducted directly with the audio files, rather than transcriptions. Such analysis preserves inflection, volume and other attributes of conversation that assist in coding.

We will conduct a series of communication analyses. The first analysis will be to content code the visit to determine all the health topics discussed in the visit. This will provide us with an overview of the conversation and will allow us to see how long providers and patients discuss genetic test results and family history and to see what other topics they discuss in their visit. The results of the content coding will provide us with graphical output in a color-coded manner that will allow us to easily see the pattern in which various health topics are discussed.

Our second analysis will be to analyze the quality of the discussions by measuring how the providers and patients exchange information regarding genetic test results and family history. Our third analysis will be measuring how providers and patients engage in decision-making based on the genetic test results by using a coding tool modeled after Braddock's Informed Decision Making model.²⁹ This measure will analyze whether there were discussions about: 1) patient role in decision making, 2) clinical issue or nature of the decision, 3) alternatives, 4) pros and cons of a decision, 5) uncertainty with decision, 6) exploring patient preferences, and assessing patient understanding.

[name] at Duke University will oversee the coding of audio recordings using the ENCOUNTER software system. Once the coding of the disclosure conversations is completed, the relational database will be exported to Drs. [name] and [name] for analysis.

Drs. [name] and [name] will obtain IRB approval at their own institutions separately for their role in this project.

Quantitative Analyses

A statistician will lead quantitative analyses. Descriptive statistics will be used to characterize physicians and patients in terms of demographic variables, motivations for participating in this study, and disclosure preferences. Descriptive statistics will also be used to characterize patients in terms of genetic literacy and comprehension, the psychological impact and personal utility of testing, and response to the information in the following domains: (a) communication with family and/or other health care providers, (b) changes in insurance purchasing behaviors or intentions, and (c) changes in health behaviors, health care utilization or behavioral intentions (e.g., diet, exercise). For measures where we have both baseline and follow-up survey data we will use standard pre-post analyses (e.g., paired t-tests, repeated measures analyses) to assess whether significant changes occurred in these domains following receipt of test results.

An initial step in our quantitative data analytic plan will be to determine potential differences between the two groups of respondents coming from a primary care setting and a cardiology clinic. Given that those from the primary care clinic do not have any particular underlying condition for which a genetic test is being ordered (unlike the patients with cardiomyopathy), it will be important to determine whether patients from these two groups can be pooled across analyses or should be analyzed separately. We will therefore examine whether respondents from the two clinics differ at baseline on key demographic characteristics as well as on our main outcomes of interest (e.g., disclosure preferences).

Economic Analysis of Utilization Data

